### 3.1. Primary objective

To determine the sensitivity of ICG fluorescence imaging alone for SLN detection compared to a combination of ICG and standard tracer.

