Early validation studies used ICG alone with reports of identification rates in excess of 90%. Subsequent practice has favoured a combination of ICG with either blue dye or radioisotope that allows both conventional and fluorescent visualisation of the lymphatic vessels and nodes. These have all shown high levels of nodal recognition by fluorescence with few nodes (<5%) being classified as blue and/or hot but not fluorescent. The ICG-10 study confirmed that combined nodal sensitivity is higher for blue dye and ICG (95.0%) compared with the standard combination of blue dye and radioisotope (73.1%).

Recent studies have shown high levels of concordance (>90%) for SLN detection not only between ICG and blue dye but also ICG and radioisotope. Fluorescence imaging provides at least equivalent detection rates but offers an additional dimension to the technique of SLN biopsy and is safe with in frequent allergic reactions. The combination of ICG with a standard tracer agent represents a transition phase and we now wish to explore ICG as a sole tracer having accrued clinical experience with its usage. In a comparison of ICG as a sole tracer versus radioisotope performed in Japan identification rates for ICG alone and radiocolloid were 98.7% and 96.7% respectively. ICG combines many of the advantages of blue dye and radioisotope without the disadvantages. Tracer combinations with dual localisation are more expensive and inconvenient than ICG alone but not necessarily associated with improved accuracy that is significant in terms of clinical outcomes.

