### 3.6. Table of endpoints/outcomes

Objectives	Outcome Measures	Timepoint(s) of evaluation of this outcome measure (if applicable)
Primary Objective To determine the sensitivity of fluorescence imaging alone for SLN identification compared with a combination of ICG and a standard tracer (blue dye or radioisotope)	Percentage of patients with successful identification of the SLN using ICG alone or combined with a standard tracer, stratified by cohort	At the time of SLN biopsy
Secondary Objectives Procedural node positivity rates	Proportion of SLN biopsy cases with tumour deposits in at least one node (including macrometastases, micrometastases and isolated tumour cells)	Post-surgery, when histopathology results are available
Adverse events from SLN biopsy	Seroma formation Cutaneous staining Other adverse reactions to tracers	2 weeks and 3 months

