## Biopsy results

- Staining characteristics of each lymph node will be documented as blue, radioactive, or fluorescent (or a combination).

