## **8. TRIAL TREATMENTS**

### **8.1. Name and description of trial treatments**

Participants in each Cohort will be randomised to ICG plus additional tracer (standard care) or ICG alone (intervention).

After randomisation, participants in Cohort 1 will undergo either routine radiocolloid injection 2 hours prior to surgery followed by an injection of 2ml of 0.5% ICG (intra-dermal/subareolar) at the time of surgery (standard care) or an injection of 2ml of 0.5% ICG alone (intra-dermal/subareolar) (intervention). The breast will be massaged for 2 minutes before measuring levels of radioactivity in the breast and axilla with a gamma probe and detection of nodes using the fluorescence PDE camera.

Participants in Cohort 2 will either be injected with 2mls of 2.5% Patent Blue dye followed by an additional 2mls 0.5% ICG (standard care) yielding a total injectate volume (blue dye/ICG) of 3mls or 2mls 0.5% ICG alone (intervention). The fluorescence PDE camera will then be used to observe the subcutaneous lymphatic streams with fluorescent imaging.

Following surgical dissection and excision, staining characteristics of each lymph node will be documented as blue, radioactive, or fluorescent (or combination thereof). The gamma probe and fluorescence PDE camera will be used to check for absence of any residual activity or fluorescence within the axilla. The time from incision to completion of node excision will be recorded in minutes.

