#### 9.2.1. Summary of baseline data and flow of patients

**No adjustment for baseline characteristics will be required**

#### 9.2.2. Primary outcome analysis

The primary analysis will be performed on the Intention to treat population, for each cohort (Cambridge/ Dundee) separately. As this is not a hypothesis generating trial, all analysis will be exploratory.

Within each group, the number of SLNs for each patient will be recorded numerically in the following categories:

	Study Arm	
Number of SLNs	ICG plus radioisotope or blue dye (standard care)	ICG alone (intervention)
Fluorescence only		
Radioisotope plus fluorescence		
Radioisotope only		
Blue dye plus fluorescence		
Blue dye only		

Pathological exam metastases		
------------------------------	--	--

The proportion of patients within each designated category will be recorded and nodes found on pathological examination to contain metastases documented. Comparison is performed on a procedural basis (proportion of patients with a positive node) using logistic regression with patient positive yes/no.

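### The primary objective says sensitivity but the outcome is a patient-level identification rate; the ICG misses recorded in the standard-care arms are tabulated but not turned into an estimate

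*Protocol*

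**What the plan says.** Sensitivity is the word used for the primary aim in the Trial Summary, in section 3.1 ("To determine the sensitivity of ICG fluorescence imaging alone for SLN detection compared to a combination of ICG and standard tracer"), in section 3.6 and in the pilot rationale of section 9.1. The outcome measure beside that objective in section 3.6 is "Percentage of patients with successful identification of the SLN using ICG alone or combined with a standard tracer, stratified by cohort". The hypothesis in section 3 speaks of detection rates.

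Under sections 4 and 8.1, patients in the intervention arms receive ICG and no other tracer. Patients in the standard-care arms receive ICG plus isotope (Cambridge) or ICG plus blue dye (Dundee). Each excised node is classed by the tracer or tracers it took up (sections 7.7 and 8.1).

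The table in section 9.2.2 has five tracer rows, among them isotope only and blue dye only. Its use is described thus: "The proportion of patients within each designated category will be recorded and nodes found on pathological examination to contain metastases documented." Section 9.2.3 says the same for nodes. The efficacy comparisons specified are two logistic regressions, on patient positive yes/no (9.2.2) and node positive yes/no (9.2.3). Section 3.6 defines node positivity by tumour deposits.

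**The concern.** Sensitivity needs a denominator that includes the nodes the test missed. With ICG as the only tracer, a missed node is not seen, so the ICG-alone arms supply no such denominator. Appendix 1 provides for random axillary sampling, but only when ICG identifies no SLN at all, and that sampling is not a reference tracer.

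The information on ICG misses sits in the standard-care arms, where a node can be blue or hot without being fluorescent. The Background relies on this measure from earlier work, reporting "few nodes (<5%) being classified as blue and/or hot but not fluorescent". The plan counts such nodes but defines no proportion, interval or within-patient summary from them.

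Section 9.1 says the pilot should inform the clinically significant difference and the size of a larger trial. What the second tracer adds to ICG bears directly on that. If the objective keeps the word sensitivity, a high identification rate may also be reported as though it showed high nodal sensitivity.

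**Working it through.** **Which tracer rows of the 9.2.2 table can be non-zero**

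| Row | ICG alone | ICG + isotope | ICG + blue dye |
|---|---|---|---|
| Fluorescence only | yes | yes | yes |
| Isotope plus fluorescence | no | yes | no |
| Isotope only | no | yes | no |
| Blue dye plus fluorescence | no | no | yes |
| Blue dye only | no | no | yes |

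One row of five can be filled in the ICG-alone arms. In each standard-care arm three can, one of which counts nodes without fluorescence.

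**Identification rate and nodal sensitivity are different quantities.** Let s be nodal sensitivity and m the number of nodes per patient. If nodes are independent, the chance that at least one is found is 1 − (1 − s)^m. The protocol does not give m; I assume 1 to 3.

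| s | m = 1 | m = 2 | m = 3 |
|---|---|---|---|
| 95% | 95% | 99.8% | 99.99% |
| 85% | 85% | 97.8% | 99.7% |
| 75% | 75% | 93.8% | 98.4% |

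For example, 1 − 0.25² = 0.9375. With two or three nodes per patient, a nodal miss rate of 15% leaves the identification rate near 98% or above. The Background keeps the two apart as well: it cites combined nodal sensitivities of 95.0% and 73.1%, and separately identification rates of 98.7% and 96.7%.

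**Sample size.** The stated 100 is 2 cohorts × 2 arms × 25. It rests on annual caseload (section 9.1), so there is no power calculation to reproduce.

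**Precision of the paired figure.** Inputs: 25 standard-care patients per cohort (section 4); m from 1 to 3 (assumed); about 95% of nodes fluorescent (assumed, in line with the Background's figure of under 5% non-fluorescent). The exact (Clopper–Pearson) limits for x of n are the 2.5% point of Beta(x, n − x + 1) and the 97.5% point of Beta(x + 1, n − x).

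| m | Nodes, 25 × m | Fluorescent, 0.95 × n rounded | Exact 95% CI |
|---|---|---|---|
| 1 | 25 | 24 | 79.6–99.9% |
| 2 | 50 | 48 | 86.3–99.5% |
| 3 | 75 | 71 | 86.9–98.5% |

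These limits treat nodes as independent. Clustering within patients would widen the intervals for m above 1.

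**Precision of the between-arm identification difference.** For scale only, take the Background's 98.7% and 96.7%, which compared ICG with radiocolloid and not this trial's arms. With 25 per arm the approximate 95% half-width is 1.96 × √(0.987 × 0.013/25 + 0.967 × 0.033/25) = 0.083, or about 8.3 percentage points.

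**The case against.** The strongest reply is that section 3.6 makes the objective operational. The percentage of patients with an SLN identified has patients as its denominator, needs no reference tracer and can be estimated in all four groups. Complete failure of ICG in a patient is visible and leads to axillary sampling under Appendix 1. This stands. A reader might infer that the trial cannot estimate its primary quantity at all; that is true only of strict nodal sensitivity, not of the stated outcome measure.

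The absence of a second tracer in the ICG-alone arms is also the intervention itself. The Background describes the combination as transitional and sets out to study ICG as sole tracer. The documents do not support calling this a design fault.

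A reader might also infer that the paired data go unused. They do not: both patient and node proportions by category are recorded, and node histology is kept alongside staining (section 10.1). A point estimate follows from adding rows. The protocol calls all analysis exploratory and defers detail to an SAP that is not at hand, where interval methods often belong. Even so, section 9.2.2 already fixes the primary comparison, and fixes it on metastatic positivity. The gap is therefore in what the protocol states, not only in detail left for later.

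Finally, the paired figure is not a direct estimate of the sensitivity of ICG used alone. The surgeon sees both signals, nodes taken up by neither tracer stay unknown, and the combination scores 100% by construction when the denominator is every tracer-identified node. This stands too, and it limits what the added analysis may be called.

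**Conclusion.** The objective is misnamed, and the analysis sections produce neither a between-arm comparison of identification nor an estimate, with uncertainty, of how often ICG misses a node that the second tracer finds. The first is a correction of wording and of the reported contrast. The second is a supporting analysis that the pilot's own purpose calls for.

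The 50 standard-care patients, 25 per cohort, can supply it. The lower 95% limit would be about 80% to 87% per cohort, assuming 1 to 3 nodes per patient, about 95% fluorescent and no clustering. That is modest precision but usable for planning. The result would describe ICG relative to the union of tracers with a second tracer present, and could not rate the combination.

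**What to change.** 1. In the Trial Summary and in sections 3.1 and 3.6, reword the primary objective as the SLN identification rate by arm and cohort, and bring section 9.1 into line. In section 9.2.2 make this the between-arm primary quantity, reported per cohort as a difference with a confidence interval.
2. Add a supporting analysis to section 9.2.2, for each standard-care arm:
   - fluorescent nodes divided by all tracer-identified nodes, with a patient-clustered 95% CI;
   - the proportion of patients with at least one fluorescent SLN, among those with any tracer-identified SLN;
   - the proportion of patients, and of metastatic nodes, found only by blue dye or isotope.
3. Label item 2 as ICG detection relative to the union of tracers, measured with the second tracer present. State that it is not the sensitivity of ICG used alone and does not assess the combination.

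The cost is a change of wording, one reported contrast and one labelled analysis. The node staining and histology are already to be recorded on the CRF, so no added patients, procedures or data collection are required.

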### 3.2. Secondary objectives

To determine procedural and node specific positivity rates for intervention and standard care.

### 3.3. Outcome measures/endpoints

See section 3.6

### 3.4. Primary endpoint/outcome

See Section 3.6

### 3.5. Secondary endpoints/outcomes

See Section 3.6

### 3.6. Table of endpoints/outcomes

Objectives	Outcome Measures	Timepoint(s) of evaluation of this outcome measure (if applicable)
Primary Objective To determine the sensitivity of fluorescence imaging alone for SLN identification compared with a combination of ICG and a standard tracer (blue dye or radioisotope)	Percentage of patients with successful identification of the SLN using ICG alone or combined with a standard tracer, stratified by cohort	At the time of SLN biopsy
Secondary Objectives Procedural node positivity rates	Proportion of SLN biopsy cases with tumour deposits in at least one node (including macrometastases, micrometastases and isolated tumour cells)	Post-surgery, when histopathology results are available
Adverse events from SLN biopsy	Seroma formation Cutaneous staining Other adverse reactions to tracers	2 weeks and 3 months

## 4. TRIAL DESIGN

This is a multicentre (two site), randomised, controlled trial. Participants will be recruited within two cohorts, one cohort at each site. Each cohort consists of parallel groups, with two treatment arms, intervention versus standard care. A total of 100 participants will be randomised, 25 in each group.

The treatment arms for each cohort are as follows:

Cohort 1 (Cambridge)

1. ICG 2mls 0.5%

2. ICG 2mls 0.5% combined with radioisotope Technetium^99 nanocolloid, 20 MBq

#### Cohort 2 (Dundee)

1. ICG 2mls 0.5%
2. ICG 2mls 0.5% combined with Patent Blue dye 2mls 2.5%

Patients will continue with standard care for further treatment of their condition.

## 5. TRIAL SETTING

This study will recruit patients from 2 large UK teaching hospitals with high volumes of breast cancer patients. Participants will be identified from the breast cancer service at these hospitals and may include at weekly multi-disciplinary team meetings attended by surgeons, radiologists, pathologists, breast care nurses and research staff.

## 6. PARTICIPANT ELIGIBILITY CRITERIA

### 6.1. Inclusion criteria

- Female
- Over 18 years of age
- Biopsy proven invasive breast cancer
- Tumour(s) measuring < 5cm in radiological size
- No record of clinical or sonographic evidence of abnormal axillary lymph nodes
- Planned SLN biopsy to be carried out as per local standard care using ICG plus radioactive tracer (Cambridge only) or ICG plus Patent Blue Dye (Tayside only)

### 6.2. Exclusion criteria

- Neoadjuvant chemotherapy
- Prior ipsilateral axillary surgery or breast excision biopsy
- Pregnant or breast feeding

Allergy to the tracers, pregnancy or breast feeding are not described as exclusion criteria as these patients will be excluded from SLN biopsy standard care.

## 7. TRIAL PROCEDURES

### 7.1. Recruitment

100 female adults,  $\geq$  18 years of age with biopsy proven invasive breast cancer will be randomised.

Sites will be informed when the target number of study participants has been reached and will be instructed not to recruit any further participants. All participants already consented to take part at this point will go forward to randomisation and will be followed until the end of the trial.

Sites will maintain a recruitment log to track potentially eligible patients who are approached about the trial but are not randomised. This data is required for the Consolidated Standards of Reporting Trials (CONSORT). Anonymised information on participants who are not randomised will include:

- Age
- Whether the patient consented

- The reason the patient was not eligible for trial participation or if they are eligible but declined, with reason for declining if provided

#### **7.1.1. Participant identification**

Identification of potentially eligible participants will be a member of the clinical team. The staff will identify patients within the breast cancer service at weekly breast MDT meetings or clinic appointments who have been diagnosed with invasive breast cancer and scheduled for routine SLN biopsy as part of primary surgical management.

#### **7.1.2. Screening**

No trial specific screening procedures are required other than to confirm participants meet the inclusion criteria.

#### **7.1.3. Ineligible participants**

Where an individual is found to be ineligible for trial participation, they will be thanked and reasons for ineligibility fully explained. Any queries or questions will be answered by an appropriate member of the research team. If ineligibility is related to an incidental finding which is clinically significant, it will be reported to the participant's GP and/or consultant by the CI or Site Principal Investigator (PI), with consent of the individual.

#### **7.1.4. Payment**

No payment will be provided to participants as all assessments will be carried out either whilst already in hospital as an inpatient/day case or by telephone consultation after discharge.

### **7.2. Consent**

The PI retains overall responsibility for the conduct of research at their site and this includes taking of informed consent at each site. They must ensure that any person delegated responsibility for seeking informed consent process is duly authorised, trained and competent to participate according to the ethically approved protocol, principles of GCP and Declaration of Helsinki.

Participants will receive a copy of the Participant Information Sheet (PIS) and ICF and will be given at least 24 hours to consider participation in the trial prior to consent. Prior to consent participants will be given the opportunity to ask any questions about the trial. Where a participant requests to speak with a physician from the trial team the consent process will not be completed until the participant had spoken to the physician and had all questions answered to their satisfaction. Once a patient agrees to participate, written informed consent will be obtained and eligibility confirmed.

In Cambridge, participants will be phoned after they have received the PIS and the consent process will be completed over the phone. This is to allow the participant to be randomised and informed whether they will need to attend a clinical visit to receive the radioisotope or not. The consent process will be witnessed by a member of staff independent of the trial team. The PI (or delegate) will sign the consent form as the person receiving consent and the independent witness will sign the consent form to confirm that the consent process was followed and the participant gave their verbal consent to take part. Participants will be asked to sign the consent form when they come for their surgery. A copy of the consent form will be given to them at this point.

In Tayside, participants will complete the consent process in person when they attend for their biopsy surgery.

The original Informed Consent Form (ICF) will be filed in the TMF or Investigator Site File (ISF) and a copy will be given to the participant and a copy will be filed in the participant's medical notes.

Where a participant loses capacity to consent the participant will be withdrawn from the study. Identifiable data or tissue already collected with consent will be retained and used in the study. No further data or tissue will be collected or any other research procedures carried out on or in relation to the participant. Participants are free to withdraw from the trial at any time. The reasons, if known, will be recorded in the medical case notes and Case Report Form (CRF).

Although a participant is not obliged to give reason(s) for withdrawing prematurely, if the participant appears lost to follow up, the CI will make a reasonable effort to ascertain the reason(s), while fully respecting the individual's rights, and will demonstrate that everything possible was done in an attempt to find any participant lost to follow-up. Those lost to follow-up or withdrawn will be identified but will still be included in the analysis if they received the intervention.

#### **7.2.1. Additional consent provisions for collection and use of participant data and biological specimens in ancillary studies, if applicable**

Not applicable

#### **7.3. The randomisation scheme**

Prior to commencement of the trial, a randomisation list will be generated for both sites. Randomisation allocation will be 50:50 intervention: standard care for each cohort. The allocation arm for each participant will be placed into sealed double envelopes with the participant specific identification number on the outside; each envelope will only contain the allocation for one participant. There will be no stratification or minimisation.

At the time of consent, participants will be allocated a unique participant identification number. After consent and prior to randomisation, the exclusion criteria will be checked. This will be documented in the CRF.

Participants in each Cohort will be randomised by the PI or delegate to one of two options as detailed in Section 8. The outcome of the randomisation allocation will be recorded in the CRF.

#### **7.4. Blinding**

Pathologist and laboratory staff processing the operative specimens will be blinded to allocation. However, it is likely that pathologists and laboratory staff will be aware when Patent blue dye has been used, blue staining to specimen, or radioisotope has been used, special handling precautions required.

#### **7.5. Emergency Unblinding**

Not applicable

#### **7.6. Baseline data**

Baseline data will be collected as per Schedule of Procedures, Appendix 4 and as described below, Section 7.7. Only information directly related to the objectives and outcome measures detailed in the protocol shall be collected.

#### **7.7. Trial assessments**

Trial assessments will be performed according to the Schedule of Procedures, Appendix 4

## Baseline

- Medical History related to their breast cancer only will be reviewed to confirm eligibility
- Concomitant medications related to their breast cancer only will be reviewed to confirm eligibility
- Height and weight
- The time from injection of ICG to completion of node excision will be recorded.

